5.3 Treatments Administered

5.3.1 **Dosing Instructions**

Study drug should **NOT** be administered to individuals known to be allergic to any component of the drug.

Subjects will be instructed to take a loading dose of 10 capsules (300 mcg) of study drug per day on Days 1, 2 and 3 at bedtime after fasting for at least 3 hours following dinner, with any nonalcoholic liquid, by the oral route. On Days 4-27, subjects will take a maintenance dose of 2 capsules per day at bedtime unless otherwise directed. Patients should remain fasted for at least 3 hours after administration of study drug.

Study drug will be provided in containers labeled as investigational study drug as per the Packaging and Labeling below in Section 5.9. The interactive response technology (IRT) will dispense an appropriate bottle configuration to each patient per the dosing requirements. Each bottle will contain either active drug or a matching placebo.

Drug accountability will be performed at each visit until the end of the 28-day treatment period. All procedures being performed during the course of this clinical study are listed sequentially by visit in Section 7: Study Activities, and may be found as a table in APPENDIX 1: Schedule of Events.

5.3.2 Dose Reduction and Stopping Rules

Although hypercalcemia is unlikely given the extensive prior experience with Rayaldee (CTAP101 Capsules), any subject who exhibits a confirmed serum total calcium >10.5 and \leq 11.0 mg/dL (corrected for serum albumin) based on blood samples obtained on Days 7 and 14 will reduce the daily maintenance dose by one capsule (from 60 mcg to 30 mcg) starting at Day 21. The dose will similarly be reduced based on blood samples obtained on Days 7 and 14 if serum total 25D is confirmed to exceed 100 ng/mL, the maximum targeted level in the FDA-approved Package Insert for Rayaldee (see APPENDIX 2.), starting at Day 21.

Subjects who exhibit confirmed serum total calcium >11.0 mg/dL (corrected for serum albumin) based on blood samples obtained on Days 7, 14 and 21 will suspend dosing until normalization of serum calcium at which time (if applicable) dosing will be resumed at one capsule per day (30 mcg per day). Subjects will be requested to return to the clinic on the earliest possible day of their next scheduled visit (eg, Day 12 for the Day 14 visit) for the confirmatory blood draw.

Subjects who develop severe (CTCAE \geq 3) abnormalities (low or high) of serum phosphorus, uric acid or plasma iPTH will be withdrawn from study drug treatment but will continue in the study.

Enrollment of subjects into the study will be paused if mortality in the treatment arm is $\geq 7\%$ higher compared to the placebo arm until the Data Safety Monitoring Board (DSMB) makes an assessment about causality, and may resume once the DSMB deems it acceptable to continue (if applicable).

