The efficacy was confirmed in a larger phase 3 program with nearly all subjects (97%) treated with CTAP101 Capsules who completed the program without a major protocol deviation achieving a normal serum total 25D level and with 50% of such subjects achieving a mean reduction in plasma iPTH from baseline of at least 30%. Fewer than 9% of placebo subjects achieved a 30% reduction in plasma iPTH or achieved a normal 25D level.

CTAP101 Capsules did not cause significant adverse effects on serum calcium or phosphorus. Treatment-emergent adverse events (TEAEs), including those related to the investigational study drug, were comparable across treatment groups, except for hyperphosphatemia which was observed in four subjects, none of which was considered by the investigator to be related to the investigational study drug. Subjects in phase 3 trials who were treated with CTAP101 Capsules experience a mean increase in serum calcium of 0.2 mg/dL during a 26-week treatment period compared with a mean increase of 0.1 mg/dL in subjects treated with placebo. Most (74%) of the subjects treated with CTAP101 Capsules received a dose of 60 mcg/day. A total of 4.2% of the active-treated subjects and 2.1% of placebo-treated subjects experienced at least 1 elevation in serum calcium above the upper limit of normal (10.5 mg/dL), none of which were clinically significant.

For all clinical studies, the adverse event (AE) profiles did not identify any events specific to CTAP101 Capsules. After both single and repeat-dose administration, CTAP101 Capsules were generally well-tolerated. The overall treatment-emergent AE profile in the phase 3 program was comparable between CTAP101 Capsules and placebo groups. Subjects receiving CTAP101 Capsules had a greater increase in mean serum corrected calcium (P<0.001) than placebo patients (0.2 versus 0.1 mg/dL); for serum phosphorus, subjects receiving CTAP101 Capsules had a greater mean increase than placebo patients (0.2 versus 0.1 mg/dL).

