6.4 Clinical Laboratory Tests

6.4.1 Laboratory Parameters

Blood will be drawn at Screening and on Days 7, 14, 21 and 28 and analyzed as specified in Table 2. Samples also will be collected for analyses of biomarkers associated with SARS-CoV-2 infection, host immune status and vitD metabolism.

All serum calcium values will be adjusted for serum albumin level of <4.0 g/dL.

All clinically significant abnormal laboratory values should be recorded as AEs and the investigator will follow-up (FU) according to Section 6.7.6 Clinical Significance.

Subjects will be in a seated or supine position during blood collection.

OPKO Pharmaceuticals, LLC Page 36 of 82

Table 2List of Laboratory Tests

Hematology:	Serum Chemistry:
Hematocrit	Albumin
Hemoglobin	Alkaline phosphatase
Platelet count	Alanine aminotransferase (ALT)
Red blood cell count	Aspartate aminotransferase (AST)
White blood cell count	Blood urea nitrogen
Peripheral blood neutrophils	Total calcium (corrected)
Peripheral mononuclear monocytes	Carbon dioxide
	Chloride
Serum b-hCG Pregnancy Test (only for females of	Creatinine
childbearing potential, defined as either not surgically sterile	Estimated glomerular filtration rate (eGFR) ²
or not diagnosed as postmenopausal) ¹	Glucose
	Lactate dehydrogenase
Biomarkers, PD and PK parameters:	Magnesium
	Phosphorus
Plasma iPTH	Potassium
Serum total 25-hydroxyvitamin D (25D) (blinded)*	Sodium
	Total bilirubin
	Direct bilirubin
	Total cholesterol
	Total protein
	Triglycerides
	Uric acid
*Data will not be available until after database lock.	Urine Pregnancy Test (only for females of childbearing potential, defined as either not surgically sterile or not diagnosed as postmenopausal)

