7.5 Visit 3 (Day 14 ± 2)

Activities to be performed during site visit:

- Review of concomitant medications.
- AE assessment.
- VS assessment.
- ECG (prolonged QT-interval will be referred to a Cardiologist for review).
- Blood samples will be obtained for the following analyses:
 - Hematology, serum chemistry (full panel and eGFR determination) (see Table 2);
 - 0
 - Plasma iPTH and serum 25D; and,
- Urine pregnancy test for females of childbearing potential (a positive test result will be confirmed with a serum b-hCG test).
- Study drug reconciliation/compliance review with subject (study drug returned to subject after visit review).
- Diary review with subject.
- Subject will self-administer 2 study drug capsules at bedtime, unless otherwise directed, after fasting for at least 3 hours following dinner and record the dose in the diary. Subject should remain fasted for at least 3 hours after administration of study drug.
- Subject will assess and record in the diary at bedtime the severity of COVID-19 symptoms and quality-of-life using the FLU-PRO Plus[©] questionnaire.

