7.6 Days 15-20

- No study site visits.
- Subject will self-administer 2 study drug capsules, unless otherwise directed, each day at bedtime after fasting for at least 3 hours following dinner and record the doses in the diary. Subject should remain fasted for at least 3 hours after administration of study drug.
- Subject will assess and record in the diary each day at bedtime the severity of COVID-19 symptoms and quality-of-life using the FLU-PRO Plus[©] questionnaire.

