7.7 Visit 4 (Day 21 ± 2)

Activities to be performed during site visit:

- Review of concomitant medications.
- AE assessment.
- VS assessment.
- Blood samples will be obtained for the following analyses:
 - Hematology, serum chemistry (full panel and eGFR determination) (see Table 2);

0

• Plasma iPTH and serum 25D; and,

- 0
- Urine pregnancy test for females of childbearing potential (a positive test result will be confirmed with a serum b-hCG test).
- Study drug reconciliation/compliance review with subject (study drug returned to subject after visit review).
- Diary review with subject.
- Subject will self-administer 2 study drug capsules, unless otherwise directed, at bedtime after fasting for at least 3 hours following dinner and record the dose in the diary. Subject should remain fasted for at least 3 hours after administration of study drug.
- Subject will self-assess and record in the diary at bedtime the severity of COVID-19 symptoms and quality-of-life using the FLU-PRO Plus[©] questionnaire.

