Patients randomized to RAYALDEE experienced a greater mean (SE) increase in serum calcium (P<0.001) than patients randomized to placebo [i.e., 0.2 (0.02) mg/dL on RAYALDEE versus 0.1 (0.03) mg/dL on placebo from baseline to trial end]. Six subjects (2%) in the RAYALDEE treatment group and no subjects (0%) in the placebo group required dose reductions for protocol-defined hypercalcemia (two consecutive serum calcium values greater than 10.3 mg/dL). A total of 4.2% of RAYALDEE treated subjects and 2.1% of placebo treated subjects experienced at least one elevation in serum calcium above the upper limit of normal (10.5 mg/dL).

Increase in Serum Phosphorus

Patients randomized to RAYALDEE experienced a greater mean (SE) increase in serum phosphorus than patients randomized to placebo [i.e., 0.2 (0.03) mg/dL on RAYALDEE versus 0.1 (0.04) mg/dL on placebo from baseline to trial end]. One subject (0.4%) in the RAYALDEE treatment group met protocol-defined hyperphosphatemia (two consecutive serum phosphorus values greater than 5.5 mg/dL deemed to be study drug related) compared to no subjects in the placebo group. A total of 45% of RAYALDEE treated subjects and 44% of placebo treated subjects experienced at least one elevation in serum phosphorus above the upper limit of normal (4.5 mg/dL).

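### The one-capsule reduction for confirmed calcium above 10.5 and up to 11.0 mg/dL is fixed at Day 21, later than needed when a Day 7 elevation is confirmed at Visit 3

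*Protocol*

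**What the plan says.** Protocol Section 5.3.2, repeated in the synopsis, sets two rules for raised calcium (corrected for albumin).

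- Confirmed value above 10.5 and up to 11.0 mg/dL, from the Day 7 and Day 14 samples: the subject "will reduce the daily maintenance dose by one capsule (from 60 mcg to 30 mcg) starting at Day 21". The same start day applies to confirmed 25D above 100 ng/mL.
- Confirmed value above 11.0 mg/dL, from the Day 7, 14 and 21 samples: the subject "will suspend dosing until normalization of serum calcium". No start day is fixed. This paragraph also asks subjects to come back on the earliest day of the next visit window for the confirmatory draw, with Day 12 for the Day 14 visit as its example.

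Sections 7.5 and 7.7 place Visit 3 at Day 14 ± 2 and Visit 4 at Day 21 ± 2. Maintenance dosing runs from Day 4 to Day 27 (Section 5.3.1). The visit schedule already lets the dose change between visits: for Days 15–20, "Subject will self-administer 2 study drug capsules, unless otherwise directed, each day at bedtime" (Section 7.6).

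**The concern.** The calcium rule acts on a calendar day and not on the confirmed result. A subject whose elevation is already confirmed is left on the full dose until Day 20, and no reason is given. The neighbouring rule for calcium above 11.0 mg/dL has no such wait, so acting on confirmation is evidently workable in this trial. The package insert in Appendix 2 (its Section 2.2) advises suspending the drug when calcium is consistently above the normal range. The protocol only halves the dose in this band, and then delays the halving.

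A second difficulty depends on how the sampling days are read. If Day 7 and Day 14 are two alternative first elevations, a Day 14 elevation is confirmed at Visit 4, and the stated start may be past before the result arrives. If they are a first sample and its confirmation, that case does not arise, and the delay described above applies to every triggered subject.

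**Working it through.** The plan gives no figure on this point to reproduce. The check is day arithmetic, taking Day 21 as the calendar day.

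**Inputs**

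- Visit 3 draw: Days 12–16 (Section 7.5). Visit 4 draw: Days 19–23 (Section 7.7).
- Full dose 60 mcg, reduced dose 30 mcg, last dose on Day 27 (Sections 5.3.1 and 5.3.2).
- Each 60 mcg dose adds about 0.6 ng/mL of 25D (Section 3.2).
- Laboratory turnaround *t*: not stated. Samples are shipped to a central laboratory (Section 6.4.2). I assume 1–3 days.

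**Day 7 elevation confirmed at Visit 3**

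The result is available on day *draw + t*. Full doses still taken from that day through Day 20 number 21 − (*draw + t*), and each exceeds the reduced dose by 30 mcg.

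- Earliest case: draw on Day 12, *t* = 1, result on Day 13. 21 − 13 = 8 doses; 8 × 30 = 240 mcg.
- Latest case: draw on Day 16, *t* = 3, result on Day 19. 21 − 19 = 2 doses; 2 × 30 = 60 mcg.
- The protocol's own example, a Day 12 draw, at *t* = 1–3: 8, 7 or 6 doses, or 240, 210 or 180 mcg.
- Removed by the rule as written: Days 21–27 = 7 doses; 7 × 30 = 210 mcg.

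**Day 14 elevation confirmed at Visit 4, if the rule covers it**

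A Day 21 start can be met only if *draw + t* ≤ 21.

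| Draw day | Turnaround at which Day 21 can be met |
|---|---|
| 19 | up to 2 days |
| 20 | up to 1 day |
| 21 | same day only |
| 22 or 23 | never |

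**Size in 25D**

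Halving one dose removes 0.6 × 30/60 = 0.3 ng/mL. For 2–8 doses this is 0.6–2.4 ng/mL, against the roughly 59–74 ng/mL that Section 3.2 expects after maintenance dosing from a baseline near 25 ng/mL.

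**Subjects affected**

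The package insert (Appendix 2, its Section 6.1) reports for the two pivotal studies: "Six subjects (2%) in the RAYALDEE treatment group and no subjects (0%) in the placebo group required dose reductions for protocol-defined hypercalcemia", with 285 treated and 144 placebo subjects. 6/285 = 2.1%, exact 95% CI 0.78%–4.53%. Applied to 80 active subjects: 80 × 0.021 = 1.7, range 0.6–3.6. This rate is an assumption here, because those studies counted two consecutive values above 10.3 mg/dL, treated for longer and used no 900 mcg loading dose.

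**The case against.** **Day 21 is not arbitrary.** If the two sampling days mean a first value and its confirmation, Day 21 is the next site visit after confirmation, and no visits fall on Days 15–20. That reading has support. Under the alternative reading, a first value above 11.0 mg/dL on Day 21 would be confirmed at Visit 5 (Day 28 + 2), after the last dose, and could not lead to suspension. It removes the Day 14 difficulty but not the delay after a Day 7 elevation. The protocol does not offer this reason, and it already allows dose instructions between visits.

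**Blinding.** Section 6.6 gives an unblinded safety monitor the task of spotting hazards such as hypercalcemia, and Section 5.12 blinds laboratory data in broad terms, though text may be missing there. If only the calcium cut moves, a Day 21 cut points more clearly to high 25D, and so to active drug, for anyone who does not see calcium. That stands, but weakly. Table 2 marks 25D as blinded and does not mark calcium. Sections 6.7.6 and 6.9 have investigators judging and acting on laboratory changes, and a site that sees calcium can already tell the two kinds of cut apart. The calcium cut itself says little about the arm: "A total of 4.2% of the active-treated subjects and 2.1% of placebo-treated subjects experienced at least 1 elevation in serum calcium" above 10.5 mg/dL in phase 3 (Section 1.5).

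**The effect is slight.** This stands. With a half-life of about 11 days in healthy people and 25 in CKD (package insert, its Section 12.3), halving a few doses is unlikely to change calcium visibly before Day 21. Section 1.5 reports that none of the phase 3 elevations was clinically significant. Values above 11.0 mg/dL suspend dosing, and Section 6.9 lets the investigator stop the drug.

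**Stronger readings that the documents do not support.** A reader might infer that Day 21 is usually too early for a Day 14 elevation. The only instruction on confirmatory draws asks for the earliest window day, which would be Day 19 for Visit 4, and from there Day 21 can be met at up to 2 days' turnaround. Counting window days does not give a frequency. A reader might also extend the criticism to the 25D trigger. There 25D is blinded, and a common fixed day is a defensible trade-off.

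**Conclusion.** The point holds for the calcium trigger and is minor; the change is a cheap improvement. After a Day 7 elevation confirmed at Visit 3, the fixed day costs 2–8 full doses beyond the known result (60–240 mcg) at an assumed turnaround of 1–3 days, under either reading of the sampling days. The Day 14 part is conditional. If the rule covers that case, Day 21 has always passed for draws on Days 22–23; for a Day 19 draw it has passed only at 3 or more days' turnaround. About 2 active subjects would be affected, at a rate borrowed from different conditions. The documents do not support a claim of material risk to subjects.

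**What to change.** In Section 5.3.2 and the synopsis, for the calcium trigger only, replace the Day 21 start with: *starting with the first dose after the confirmed result is available*. State that the instruction goes by the same route as the suspension above 11.0 mg/dL, through the investigator or the unblinded safety monitor. Extend the request for an earliest-day confirmatory draw to this band. Keep Day 21 for the 25D trigger.

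The cost is a short wording change in two places, with the usual amendment review, and no new visit, sample or dispensing. The downsides are a phone instruction between visits for about 2 active subjects (0.6–3.6) and a weak hint of treatment arm.

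The new wording works under either reading of the sampling days.

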Although hypercalcemia is unlikely given the extensive prior experience with Rayaldee (CTAP101 Capsules), any subject who exhibits a confirmed serum total calcium >10.5 and $\leq 11.0 \text{ mg/dL}$ (corrected for serum albumin) based on blood samples obtained on Days 7 and 14 will reduce the daily maintenance dose by one capsule (from 60 mcg to 30 mcg) starting at Day 21. The dose will similarly be reduced based on blood samples obtained on Days 7 and 14 if serum total 25D is confirmed to exceed 100 ng/mL, the maximum targeted level in the FDA-approved Package Insert for Rayaldee (see APPENDIX 2.), starting at Day 21.

Subjects who exhibit confirmed serum total calcium >11.0 mg/dL (corrected for serum albumin) based on blood samples obtained on Days 7, 14 and 21 will suspend dosing until normalization of serum calcium at which time (if applicable) dosing will be resumed at one capsule per day (30 mcg per day). Subjects will be requested to return to the clinic on the earliest possible day of their next scheduled visit (eg, Day 12 for the Day 14 visit) for the confirmatory blood draw.

Subjects who develop severe (CTCAE \geq 3) abnormalities (low or high) of serum phosphorus, uric acid or plasma iPTH will be withdrawn from study drug treatment.

Enrollment of subjects into the study will be paused if mortality in the treatment arm is $\geq 7\%$ higher compared to the placebo arm until the Data Safety Monitoring Board (DSMB) makes an assessment about causality, and may resume once the DSMB deems it acceptable to continue (if applicable).

Other Evaluations:

Blood samples will be acquired periodically during the study (see APPENDIX 1: Schedule of Events). Blood samples will be assayed for: i) serum total 25D (primary efficacy measure),

	iv) plasma iPTH, v) clinical
chemistries and hematology,	
Daily as	ssessments of disease severity and

quality-of-life measures will be recorded by each subject using the FLU-PRO Plus[©] questionnaire.

Sample Size Estimation:

Primary outcome #1 (attainment of serum 25D levels at \geq 50 ng/mL): Assuming that no more than 25% of the control group will achieve an increase in serum 25D to \geq 50 ng/mL by Day 28 versus greater than 75% in the CTAP101 Capsules group, a sample size of 19 per group will provide 90% power at alpha 0.025 one sided for a Chi-square test of the two groups.

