6.4.2 Sample Collection, Storage, and Shipping

Missed blood samples should not be drawn or collected (unless the investigator considers the sample necessary for subject safety) and should be noted as "not done" in source documentation along with a reason.

A central laboratory experienced in clinical research trials will be utilized. Collection, processing, storage and shipping procedures will be performed in accordance with the instructions provided by the central laboratory. Any detailed instructions will be provided

¹ Performed at screening, and again at subsequent visits only after a positive urine pregnancy test.

² Calculated value.
Protocol CTAP101-CL-2014
CTAP101 (calcifediol) Extended-release Capsules

separately from this protocol to the laboratory. Blood samples will be collected and analyzed for clinical laboratory and **second second** biomarker tests.

The laboratory may ship specimens to other designated outside specialty facilities as appropriate. Approximately 385 mL of blood will be drawn from each subject during the course of the study. This volume will include overage/backup volume as described in the study laboratory manual. Additional blood draws may be needed for unscheduled or repeat visits. Every effort has been made to minimize the total amount of blood to be drawn. Samples are to be shipped to the central laboratory for each subject as visits are completed.

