6.9 Removal of Subjects from the Study or Study Drug / Stopping Criteria

The investigator may discontinue a subject from study drug treatment for any of the following reasons:

- A major protocol deviation occurs;
- A serious or intolerable AE occurs;
- The subject has a confirmed pregnancy;
- A clinically significant change in a laboratory parameter occurs (eg, increase in serum calcium above upper limit allowed); and,
- A clinically significant change in ECG at Visit 3 occurs as compared to baseline (eg, prolongation of QT interval).

The investigator may withdraw a subject from the study for any of the following reasons:

- The subject requests to be discontinued from the study (withdraws consent); or,
- The subject is lost to follow-up.

Subjects who develop severe (CTCAE \geq 3) abnormalities (low or high) of serum phosphorus, uric acid or plasma iPTH will be withdrawn from study drug treatment.

Enrollment of subjects into the study will be paused if mortality in the treatment arm is $\geq 7\%$ higher compared to the placebo arm until the DSMB makes an assessment about causality, and may resume once the DSMB deems it acceptable to continue (if applicable).

No subject replacement is planned. All subjects withdrawn from treatment will continue in the study until study completion and perform all assessments unless consent is withdrawn. The investigator will be requested to make all reasonable efforts to obtain clinical status at FU.

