7.9 Visit 5 (Day 28 + 2) (End of Treatment/Early Termination)

Activities to be performed during site visit:

- Review of concomitant medications.
- AE assessment.
- VS assessment (weight and BMI).
- Brief PE.
- ECG (prolonged QT-interval will be referred to a Cardiologist for review).
- Blood samples will be obtained for the following analyses:
 - Hematology, serum chemistry (full panel and eGFR determination) (see Table 2);
 - Plasma iPTH and serum 25D; and,
 - 0

- Urine pregnancy test for females of childbearing potential (a positive test result will be confirmed with a serum b-hCG test).
- Study drug reconciliation/compliance review with subject (treatment complete no further study drug dispensed).
- Diary review with subject.

Subject will assess and record in the diary at bedtime the severity of COVID-19 symptoms using the FLU-PRO Plus[©] questionnaire.

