Study drug administration - loading dose (self-administered)		X ^h	X ⁱ									
Study drug administration - maintenance dose (self-administered)			Xj	X ^j	X ^j	X ^j	Xj	X ^j	Xj			
Subject self-assessment for severity of COVID-19 symptoms and QOL using the FLU-PRO Plus [©] questionnaire (diary) ^k	х	Х	x	х	х	х	х	х	х	х	х	х

^h Study drug (10 capsules) will be administered at bedtime after fasting for 3 hours. Subject must continue to fast for 3 hours after administration of study drug.

¹ Days 2 and 3 only. Study drug (10 capsules on each day) will be administered at bedtime after fasting for 3 hours. Subject must continue to fast for 3 hours after administration of study drug.

^j Maintenance dose starting on Day 4 through Day 27 (2 capsules, unless otherwise directed, administered at bedtime after fasting for 3 hours. Subject must continue to fast for 3 hours after administration of study drug).

k Completed at Screening visit on site and thereafter once each day at bedtime (except Day 42 - once when subject wakes up).

Protocol CTAP101-CL-2014 CTAP101 (calcifediol) Extended-release Capsules

OPKO Pharmaceutcials, LLC Page 66 of 82

	Screening and (Day	Randomization -3 to 1)									Follo	ow-up
				Treatment Period (Days 1-28)					(Days 29-42)			
	Vi	sit 1		Visit 2		Visit 3		Visit 4		Visit 5 / ET		Visit 6ª
	Days -3 to 0	Day 1 ^b	Days 2-6 ^c	Day 7 (± 2)	Days 8-13 ^c	Day 14 (± 2)	Days 15-20 ^c	Day 21 (± 2)	Days 22-27 ^c	Day 28 (+ 2)	Days 29-41°	Day 42 (± 4)
Study Procedure	Screening	Randomization and initiation of treatment										
Study drug administration recorded in diary		Х	х	Х	х	х	х	х	х			
Study drug return and compliance review				Х		Х		х		Х		
Diary review				Х		Х		Х		Х		X
Laboratory Assessments												
Hematology ¹ and serum chemistry ^m	х			х		Х		х		х		
Serum ß-hCG ⁿ	X			Х		Х		Х		Х		
Urine pregnancy test				Х		Х		Х		Х		
Biomarkers, PD and PK parameters ^o	x			Х		X		Х		X		

plasma iPTH and serum total 25D;

¹ Hematocrit, Hemoglobin, Platelet count, Red blood cell count, White blood cell count, Peripheral blood neutrophils, peripheral mononuclear monocytes.

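### A corrected calcium above 11.0 mg/dL first seen at Visit 4 (Day 21) cannot trigger the mandatory suspension, because confirmation waits until Day 28 and the last dose is on Day 27

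*Protocol*

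**What the plan says.** Protocol 5.3.2 requires that subjects with a confirmed corrected calcium above 11.0 mg/dL "based on blood samples obtained on Days 7, 14 and 21 will suspend dosing until normalization of serum calcium", with a restart at 30 mcg/day where applicable. One value is not enough. The confirmatory draw is tied to the visit schedule: subjects are asked to "return to the clinic on the earliest possible day of their next scheduled visit (eg, Day 12 for the Day 14 visit"). The synopsis carries the same rule and the same instruction ("Subjects will be requested to return to the clinic on the earliest possible day of their next scheduled visit").

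The calendar after the Day 21 visit is fixed elsewhere in the Protocol. Visit 4 is Day 21 ± 2 (7.7). There are no site visits on Days 22 to 27 (7.8). The next visit is "Visit 5 (Day 28 + 2) (End of Treatment/Early Termination"), which has no early side. Appendix 1 gives the dosing period as "Maintenance dose starting on Day 4 through Day 27", in agreement with 5.3.1 and SAP 3.2.

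Two other provisions bear on the point. Section 6.9 lists among the reasons for which the investigator may stop study drug: "A clinically significant change in a laboratory parameter occurs (eg, increase in serum calcium above upper limit allowed"). Section 6.4.2, in giving the blood volume, notes: "Additional blood draws may be needed for unscheduled or repeat visits".

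**The concern.** The suspension rule names Day 21 as one of its sampling days, but its confirmation step appears to fall after the last dose for anything first found there. A site that applies 5.3.2 literally would see a calcium above 11.0 mg/dL at Visit 4, wait for Visit 5, and let the subject take every remaining dose. The restart at 30 mcg/day would be equally empty. Visit 6 is a telephone contact, and Appendix 1 shows no chemistry after Visit 5, so no scheduled sample would show whether calcium had come down.

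What is at stake is subject safety in a late, probably small group. Stopping drug would rest on the investigator's discretion in 6.9 and no longer on the obligation in 5.3.2.

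**Working it through.** **Inputs (Protocol).** Visit windows: Day 7 ± 2, Day 14 ± 2, Day 21 ± 2, Day 28 + 2 (7.3, 7.5, 7.7, 7.9). Last dose: Day 27. Maintenance dose: 60 mcg at bedtime (5.3.1). Confirmation: first day of the next visit's window (5.3.2).

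**The Protocol's own example.** Day 14 − 2 = Day 12, as 5.3.2 states.

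**Formulas.** Let s be the sample day and v the first day of the next visit's window.
- Doses taken from the sample day up to confirmation = v − s. This includes the dose on the sample day, which may precede the result.
- Doses left at confirmation = max(0, 27 − v + 1). This treats the confirmatory result as known on the day of the draw, so it is an upper limit.

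| First seen at | v | Doses taken while waiting: nominal day (range over window) | Doses left to suspend |
|---|---|---|---|
| Day 7 | 12 | 12 − 7 = 5 (3 to 7) | 27 − 12 + 1 = 16 |
| Day 14 | 19 | 19 − 14 = 5 (3 to 7) | 27 − 19 + 1 = 9 |
| Day 21 | 28 | 28 − 21 = 7 (5 to 9) | max(0, 27 − 28 + 1) = 0 |

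The zero does not depend on which day of the Visit 4 window (Days 19 to 23) the sample is taken.

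**Two readings of the rule.** If Days 7, 14 and 21 are initial samples, confirmation of a Day 21 value comes too late. If they are the samples that together form a confirmed pair, the Day 21 sample can confirm a Day 14 elevation (up to 9 doses left), but a first value at Day 21 has no mandatory route at all. The gap exists on both readings.

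**Size.** Planned total dose = 900 + 24 × 60 = 2,340 mcg. The wait after Visit 4 covers 5 × 60 = 300 mcg to 9 × 60 = 540 mcg: 300/2,340 = 12.8% and 540/2,340 = 23.1%. Through Day 20 a subject has already taken 900 + 17 × 60 = 1,920 mcg.

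**What a hold would spare.** The documents give no laboratory turnaround, so T days is an assumption. Doses spared by holding on the first result = 27 − (s + T) + 1.
- T = 1 to 2: 6 to 5 doses (360 to 300 mcg) for s = 21; from 8 (s = 19, T = 1) down to 3 (s = 23, T = 2) over the window.
- T = 3 to 5: 4 to 2 doses for s = 21; 2 to 0 for s = 23.

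These figures apply if the value is confirmed and calcium does not normalize before Day 27.

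**Repeat draw without a hold.** If the draw comes d days after the first result, confirmation is known on day s + T + d + T. With s = 21, T = 2 and d = 3 this is 21 + 2 + 3 + 2 = Day 28, again too late. With T = 1 and d = 1 it is Day 24, leaving 27 − 24 + 1 = 4 doses.

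**The case against.** The strongest reply is that sites follow the whole protocol. Section 6.9 allows drug to be stopped without confirmation and gives raised calcium as its example. Section 6.4.2 foresees extra draws, 5.3.1 lets dosing be redirected, 6.7.6 treats abnormal results as clinically significant by default, and the DSMB (6.6) has an unblinded safety monitor whose example hazard is hypercalcemia. This shows that protection exists, and that part stands. It does not repair the rule. Section 6.9 is permissive, 6.7.6 decides what counts as an adverse event, 6.4.2 does not link extra draws to calcium, and no action or timing is stated for the safety monitor.

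The second reply is that little is at stake, and this largely stands. By Protocol 3.2 each 60 mcg dose adds about 0.6 ng/mL to serum 25D, so sparing 5 to 6 doses avoids about 3.0 to 3.6 ng/mL, and 8 doses about 4.8 ng/mL. The case is also rare. In phase 3, "4.2% of the active-treated subjects and 2.1% of placebo-treated subjects experienced at least 1 elevation in serum calcium" above 10.5 mg/dL, none clinically significant (1.5). Applied to 80 active subjects, 4.2% is about 3.4, for a lower threshold and over 26 weeks. That program had no 900 mcg loading dose, so it is only a guide.

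The third reply is that a hold before confirmation treats Day 21 more strictly than Days 7 and 14, where a sample taken early in the window also waits 7 doses. That is true of the wait. But after Days 7 and 14, doses remain when confirmation comes, and after Day 21 none do. A repeat draw alone may also return its result too late.

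**Conclusion.** The concern holds. For a corrected calcium above 11.0 mg/dL first seen at Visit 4, the mandatory suspension in 5.3.2 has 0 doses to act on, on either reading of the sampling days. This follows from the Protocol's own calendar and needs no assumption. The assumed turnaround affects only how much a repair would save.

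The consequence is limited: the case should be rare, most of the planned exposure has already occurred by Day 20, and the investigator can stop drug under 6.9. Sample size, alpha, the Day 14 endpoint and the symptom analysis are untouched. It should be corrected because a mandatory safety rule ought to work on every sampling day that it names, and the correction is cheap.

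**What to change.** Add one sentence to 5.3.2 and to the synopsis, for example:

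> If corrected calcium first exceeds 11.0 mg/dL at Visit 4 (Day 21 ± 2), study drug is held when the result is received and an unscheduled confirmatory sample is taken within about 1 to 3 days, without waiting for Visit 5; if the value is not confirmed, the previous dose is resumed through Day 27.

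If the value is confirmed, the existing rule applies, with restart at 30 mcg/day only if dosing days remain. The sponsor and DSMB can set the exact interval, and should state the expected laboratory turnaround, since the benefit depends on it.

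The cost is a rare extra draw of a kind already foreseen in 6.4.2. If the value is not confirmed, the doses missed are T + d: with T = 1 to 2 and d = 1 to 3, that is 2 to 5 doses (120 to 300 mcg) for a sample on Day 21.
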